- iii. MTX: Subjects are permitted to continue MTX provided that the dose is stable for ≥ 12 weeks prior to randomization and remains stable throughout the study. Decrease in dose or discontinuation is permitted for AEs or intolerance.
- iv. Leflunomide (20 mg per day).
- v. Mycophenolate mofetil/mycophenolic acid (MMF). Note: Subjects who are receiving MMF may participate in the study only if administered as a maintenance therapy and up to a maximum of 2 g/day (or equivalent); in subjects of African ancestry, 3 g/day (or equivalent) is acceptable.
- vi. Dapsone (maximum 100 mg per day).
- c) Not applicable per Revised Protocol 03 CS (prednisone or equivalent) background therapy is permitted but not required. For subjects taking CS, the dose must be stable for ≥ 2 weeks before the screening visit, cannot exceed 40 mg/day at screening, and must remain stable until randomization. Further specifications are as follows:
 - O Topical and inhaled CS use is permitted but must follow a stable regimen throughout the study and cannot be used on an as-needed basis. Discontinuation of topical steroids should be allowed if lesions/rash resolve completely. Inhaled CS for nonlupus conditions will not count against the maximum CS dose.
 - o Patients are ineligible if they received intramuscular (IM), intra-articular (IA), intrabursal, IV, and modified-release CS use within 4 weeks prior to randomization.
- d) SOC that is allowed in this study must include at least one of the following:

Antimalarials, Immunosuppressants, or oral CS

Antimalarials and/or Immunosuppressants must have been taken for ≥ 12 weeks before the screening visit and must be at a stable dose for ≥ 8 weeks before the screening visit and remain stable until randomization and throughout study participation. Details for Antimalarials and/or Immunosuppressants are as follows:

• Antimalarials: chloroquine, HCQ, or quinacrine; monotherapy is permitted. Also see exclusion criteria below regarding HCQ dose limitation and exclusionary screening HCQ levels. Subjects on HCQ must have an ophthalmology assessment within

6 months prior to randomization, confirming no findings of HCQ induced retinal toxicity.

- Immunosuppressants (combinations of these are NOT permitted):
 - o Azathioprine (maximum 200 mg per day).
 - o 6-mercaptopurine (6-MP, maximum 1.5 mg/kg per day).
 - MTX: Subjects are permitted to continue MTX provided that the dose is stable for

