 ≥ 12 weeks prior to randomization and remains stable throughout the study.
 Decrease in dose or discontinuation is permitted for AEs or intolerance.
 - o Leflunomide (20 mg per day).
 - o Mycophenolate mofetil/mycophenolic acid (MMF). Note: Subjects who are receiving MMF may participate in the study only if administered as a maintenance therapy and up to a maximum of 2 g/day (or equivalent); in subjects of African ancestry, 3 g/day (or equivalent) is acceptable.
 - O Dapsone (maximum 100 mg per day).
- e) CS (prednisone or equivalent), as follows:
 - o For subjects taking oral CS as monotherapy, CS must have been taken for ≥ 6 weeks prior to the screening visit at a dose ≥ 7.5 mg/day and ≤ 40 mg/day prednisone (or prednisone equivalent), must be at a stable dose for ≥ 2 weeks prior to the screening visit and remain stable until randomization.
 - For subjects taking oral CS not as monotherapy, the CS dose must be stable for ≥2 weeks before the screening visit, cannot exceed 40 mg/day at screening, and must remain stable until randomization.
 - O Topical and inhaled CS use is permitted but must follow a stable regimen throughout the study and cannot be used on an as-needed basis. Discontinuation of topical steroids should be allowed if lesions/rash resolve completely. Inhaled CS for nonlupus conditions will not count against the maximum CS dose.
 - Subjects are ineligible if they received IM, IA, intrabursal, IV, and modified-release
 CS use within 4 weeks prior to randomization.

5) Other Inclusion Criteria: SLE Sub-protocol

a) Subject re-enrollment (rescreening): This study permits the re-enrollment of a subject who has discontinued the study as a pretreatment (screening) failure (ie, subject has not been randomized/has not been treated). If re-enrolled, the subject must be re-consented.

Clinical Protocol
BMS-986195
IM014029 - SLE
Branebrutinib

SLE 5.2 Exclusion Criteria

An individual who meets any of the following criteria will be excluded from participation in the SLE sub-protocol:

1) General Medical Conditions and History: SLE Sub-protocol

- a) Any major illness/condition or evidence of an unstable clinical condition (eg, renal, hepatic, hematologic, gastrointestinal, endocrine, pulmonary, immunologic, psychiatric) or local active infection/infectious illness that, in the investigator's judgment, will substantially increase the risk to the subject if he or she participates in the study.

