- x) Administration of all live vaccines is prohibited within 90 days before randomization. Administration of inactivated vaccines and nonlive vaccines, including those for influenza and SARS-CoV-2, is prohibited within 30 days before randomization. See SLE Table 6 for corresponding on-treatment and posttreatment restrictions.
- y) Treatment with DMARDs (excluding HCQ) or immunomodulators beyond required washout period before randomization; MTX treatment within 12 weeks before randomization or during the study. **HCQ whole blood concentration** > 2 μg/mL (at screening only) is exclusionary. HCQ dose > 400 mg/day, new initiation, or dose increases during treatment are not permitted.
- 6) Physical and Laboratory Test Findings: SLE Sub-protocol
 - a) Clinically significant abnormalities on chest x-ray or ECG

Clinical Protocol BMS-986195

- b) Clinically significant abnormalities in laboratory tests including the following:
 - i. Serum alanine aminotransferase (ALT) $> 2 \times ULN$
 - ii. Serum aspartate aminotransferase (AST) > 2× ULN
 - iii. Serum total bilirubin > 1.5× ULN (does not apply to subjects with Gilbert's syndrome)
 - iv. Hemoglobin < 8 g/dL (< 80 g/L) or, if due to hemolytic anemia related to SLE, < 7 g/dL (< 70 g/L)
 - v. Proteinuria > 3.0 g/day (> 3,000 mg/day) or equivalent level of proteinuria as assessed by UPCR (3 mg/mg or 339 mg/mmol)
 - vi. Estimated glomerular filtration rate (eGFR) < 50 mL/min/1.73 m² as calculated by the central laboratory
 - vii. Serum creatinine > 2.0 mg/dL (> 177 μmol/L)
 - viii. Absolute WBC count $< 2.5 \times 10^3 / \mu L$ ($< 2.5 \times 10^9 / L$)
 - ix. Neutrophil count $< 1000/\mu L$ ($< 1.0 \times 10^9/L$)
 - x. Platelet count $< 75 \times 10^3 / \mu L$ ($< 75 \times 10^9 / L$), if considered part of SLE disease activity without increased risk of bleeding
- c) Any other significant laboratory or procedure abnormalities that, in the opinion of the investigator, might pose unacceptable risk to the subject during the study
- d) Blood pressure (BP) > Grade 1 hypertension (> 159 mmHg systolic and > 99 mmHg diastolic) according to the 2018 ESC/ESH Guidelines for the management of arterial hypertension.
- e) The following exclusionary ECG observations:
 - i. QT interval with Fridericia's correction (QTcF): > 480 msec
 - ii. QRS: > 120 msec
 - iii. Complete heart block
 - iv. Left bundle branch block
 - v. Mobitz II second-degree atrioventricular block
 - vi. Atrial fibrillation or flutter

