7) Other Exclusion Criteria: SLE Sub-protocol

- a) Prisoners or subjects who are involuntarily incarcerated. (Note: under certain specific circumstances and subject to local law a person who has been imprisoned may be included or permitted to continue as a subject. Strict conditions apply and BMS approval is required.)
- b) Subjects who are employed by the Sponsor, clinical research organizations, or study site
- c) Subjects who are compulsorily detained for treatment of either a psychiatric or physical (eg, infectious disease) illness
- d) Inability to comply with the study protocol
- e) Inability to comply with restrictions as listed in Section SLE 5.3

Clinical Protocol
BMS-986195
IM014029 - SLE
Branebrutinib

SLE 5.3 Lifestyle Restrictions

Study restrictions for contraception use by WOCBP and male subjects who are partners of WOCBP (APPENDIX 4) are required for this study.

SLE 5.3.1 Meals and Dietary Restrictions

With the exception of the 8-hour fasting requirement prior to blood sample collection for lipid panel and fasting glucose blood testing, no meal or dietary restrictions are required for this study. However, subjects are advised to consume in moderation (avoiding more than a single serving a day) cruciferous vegetables, such as cabbage, brussels sprouts, watercress, etc, as well as grapefruit and Seville oranges. Quinine (tonic water), St. John's wort and herbal medications are not allowed.

SLE 5.3.2 Caffeine, Alcohol, Tobacco, and Cannabinoids

With the exception of cannabinoid products, which are not allowed, and prohibited alcohol abuse as defined by the Diagnostic Criteria for Drug and Alcohol Abuse in the DSM 5 within six months prior to randomization, and prohibited alcohol use in subjects receiving MTX therapy (see Section SLE 5.2), there are no restrictions on caffeine, alcohol, or tobacco use for this study. However, subjects who use tobacco or alcohol should be counseled for potential contraindications with nonstudy treatments as appropriate, and continued study participation should be based on investigator judgment. Subjects are advised to abstain from excessive consumption of caffeine-containing drinks.

SLE 5.3.3 Activity

With the exception of the restrictions surrounding the use of contraceptives during sexual activity mentioned above and included in the SoA (Section SLE 1.3), no activity restrictions are required for this study.

SLE 5.3.4 Screen Failures

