	Topical and inhaled CS	allowed if lesions/rash resolve	Not applicable
		completely. Inhaled CS for	
		nonlupus conditions will not	
		count against the maximum CS	
		dose	
		Must have been taken for ≥ 12	
		weeks before the screening visit	
		and must be at a stable dose for	10 1 10
A	Chl	\geq 8 weeks before the screening	12 weeks if not
Antimalarial drugs	Chloroquine and quinacrine	visit and remain stable until randomization and throughout	continuing as background SOC
		study participation. New	background SOC
		initiation or change in dose	
		during treatment is not permitted	
		Doses of > 400 mg/day are not	
		permitted	12 weeks if not
	Hydroxychloroquine (HCQ)	New initiation or dose increase	continuing as
		during treatment is not	background SOC
		permitted. Whole blood levels at	G 2 2 3
		screening must be $\leq 2 \mu g/mL$ Treatment with anticoagulant or	
		antiplatelet therapies, including	
Anticoagulant or	Anticoagulant or antiplatelet	aspirin for cardioprotection,	
Antiplatelet therapies	therapies, including aspirin	within 2 weeks prior to	2 weeks
	for cardioprotection	randomization or during the	
		study	

Protocol Amendment No.: 04

Date: 01-Dec-2021 78

SLE Table 6 Prohibited and Restricted Medications

Type of Medication	Examples of Medications	Restrictions	Required Washout Period Prior to and Postrandomization
Anti-TNF therapy	Adalimumab, certolizumab, etanercept, golimumab, infliximab, and TNF biosimilars	Prohibited during the study	3 months
Biologics	Rituximab	Prohibited during the study	12 months
	Belimumab	Prohibited during the study	6 months
	Abatacept	Prohibited during the study	6 months
	Other Biologics, including tocilizumab, anakinra		8 weeks
	IVIG	Prohibited during the study	8 weeks
Immunosuppressants (allowed) Note: combinations of immunosuppressants are not allowed	Azathioprine, 6-MP, MTX, leflunomide, MMF	Must have been taken for ≥ 12 weeks before the screening visit and must be at a stable dose for ≥ 8 weeks before the screening visit and remain stable until randomization and throughout study participation. New initiation or dose changes during treatment are not permitted.	12 weeks if not continuing as background SOC, except leflunomide 36 weeks before screening
Immunosuppressants (prohibited)	Cyclosporine, tacrolimus, thalidomide and similar (oral); topical calcineurin inhibitors (tacrolimus, pimecrolimus)	Prohibited during the study	8 weeks
O.I. D.M.D.	Cyclophosphamide	Prohibited during the study	24 weeks

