- Protocol waivers or exemptions are not allowed.
- All immediate safety concerns must be discussed with the Medical Monitor immediately upon occurrence or awareness to determine if the subject should continue or discontinue treatment.
- Adherence to the study design requirements, including those specified in the SoA (Section SLE 1.3), is essential and required for study conduct.
- All screening evaluations must be completed and reviewed to confirm that potential subjects meet all eligibility criteria before randomization. The investigator will maintain a screening log to record details of all subjects screened and to confirm eligibility or record reasons for screening failure, as applicable.
- Procedures conducted as part of the subject's routine clinical management (eg, BP, physical examination, medical history) on the day of the screening visit and obtained before signing of the informed consent may be used for screening provided the procedure meets the protocol-defined criteria and has been performed within the timeframe defined in the SoA (Section SLE 1.3).

SLE 8.1 Efficacy Assessments

The PI, or sub-investigator, designated by the PI and confirmed by the Sponsor, should perform all clinical assessments at a site visit. The sub-investigator may be a Doctor of Medicine or Doctor of Osteopathy, Physician's Assistant, or Nurse Practitioner with experience in the diagnosis and management of subjects with SLE.

All assessments should be performed or administered prior to study drug administration unless otherwise indicated. Other conditions include:

- Every effort must be made to ensure the same investigator performs all of the investigator-administered assessments for a given subject at each visit and throughout the study to minimize inter-observer variation.
- If the investigator is unable to complete the assessment at a given visit, the approved back-up investigator may complete the assessment.
- Assessments are to be conducted at approximately the same time of day throughout the duration of the study for each subject.
- Visits should be scheduled with the availability of the specific investigator managing a given subject taken into account.

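### SLE exclusion criterion 5y bars all recent or on-study methotrexate, although inclusion criterion 4d and SLE Table 6 allow stable background methotrexate

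*Combined protocol and SAP*

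**What the plan says.** Four provisions of the SLE sub-protocol bear on background methotrexate (MTX). None carries a not-applicable label.

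- **SLE 5.2, exclusion 5y.** After a first limb on DMARDs and immunomodulators, which excepts only hydroxychloroquine, a separate limb excludes "MTX treatment within 12 weeks before randomization or during the study". The lead-in to the section states: "An individual who meets any of the following criteria will be excluded from participation".
- **SLE 5.1, inclusion 4d.** MTX is listed among the immunosuppressants that may serve as background standard of care: "MTX: Subjects are permitted to continue MTX provided that the dose is stable for" at least "12 weeks prior to randomization and remains stable throughout the study".
- **SLE Table 6.** The row for allowed immunosuppressants names "Azathioprine, 6-MP, MTX, leflunomide, MMF". Its washout column reads "12 weeks if not continuing as background SOC, except leflunomide 36 weeks before screening".
- **SLE 5.3.2.** Alcohol use is prohibited for subjects on MTX, which presupposes that such subjects are in the study.

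SLE 8 adds: "Protocol waivers or exemptions are not allowed".

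**The concern.** Criterion 5y uses the same 12-week window as Table 6 but omits the condition that limits Table 6 to patients who are not continuing the drug. It also extends the ban through the study. As written, it removes the patients whom 4d and Table 6 invite.

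A site with a patient on stable MTX has two options: screen the patient out despite 4d, or randomize someone who meets an exclusion criterion in a protocol that allows no waivers. Nothing in the text addresses the conflict. The affected patients all belong to the 'yes' level of immunosuppressant use, the only SLE stratification factor (SLE 6.2). If enrolled, their status in the Per Protocol Set is unclear, because SLE 9.2 removes subjects with statistically relevant deviations and does not say whether this would be one.

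**Working it through.** The plan gives no figure to reproduce. The check compares the criteria in force.

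**Step 1: the two windows.**

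| Provision | 12 weeks before randomization | During the study |
|---|---|---|
| Inclusion 4d | MTX taken at a stable dose | MTX continued at a stable dose |
| SLE Table 6 | washout only if MTX is not continued | MTX allowed at a stable dose |
| Exclusion 5y | any MTX excludes | any MTX excludes |

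A subject who uses the 4d allowance has taken MTX throughout the 12 weeks before randomization. Any MTX in those same 12 weeks triggers 5y. The share of 4d MTX users who meet 5y is therefore 100%, and 0% satisfy both rules.

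**Step 2: can 5y be read as a washout rule for stopped MTX?** No. The reference to a required washout period qualifies the DMARD limb. The MTX limb follows a semicolon, sets its own window and extends to the treatment period. A rule meant only for discontinued MTX would not need that extension.

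**Step 3: how many agents are affected?** Criterion 4d lists azathioprine, 6-mercaptopurine, MTX, leflunomide, mycophenolate and dapsone, which makes 6. For the other 5, the DMARD limb of 5y depends on the required washout, and Table 6 waives washout when the drug continues as background therapy. Those 5 can be reconciled, so 1 of 6 is in conflict.

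**Step 4: which rule reflects the intent?** Criterion 4d, Table 6 and SLE 5.3.2 all assume MTX users take part. SLE 8.5.1 also names MTX use as a possible covariate when concomitant-drug concentrations are compared. Criterion 5y stands alone.

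**Step 5: likely origin.** The same clause appears in pSS exclusion 5dd, where it is right: pSS Table 6 prohibits MTX, with a 12-week washout. Carry-over from the pSS text is plausible, but it is an inference, and the conflict does not depend on it.

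**The case against.** The best counter-argument is that intent is not in real doubt. One stray clause stands against several consistent provisions, and the Medical Monitor or Lupus Central Review Services confirms every subject's eligibility before randomization (SLE 5). Sites would probably follow 4d. This limits inconsistency between sites, but central review works from the same contradictory text and has no waiver to grant, so a subject enrolled on MTX still meets a written exclusion.

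It can also be said that the lead-in to SLE 5.2 settles precedence: any one exclusion disqualifies, so 5y wins. Read strictly, that is correct, but it leaves the MTX allowance in 4d and Table 6 with no effect, which is plainly not intended.

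The objection on analysis carries more weight. The Full Analysis Set primary analysis and the nonresponder rule do not change, and p-values for the primary endpoint are descriptive. The Per Protocol Set may be used only as support, and SLE 9.2 does not make every eligibility deviation statistically relevant. No effect on an estimate has been shown. It is also fair that the percentages in the check restate the contradiction and do not measure its impact on enrollment.

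**Conclusion.** The contradiction is real and lies between provisions currently in force. No subject on continued background MTX can satisfy both inclusion 4d and exclusion 5y. It is a drafting error in an operative eligibility rule and should be corrected.

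Its reach is limited. It concerns one of six listed agents and leaves the primary analysis intact. The number of subjects affected is unknown, because the documents do not give the MTX share of the 60 planned, and no change in power or effect size is claimed. The conclusion rests on the wording alone and needs no outside assumption.

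**What to change.** In SLE exclusion 5y, either delete the MTX clause or restrict it to MTX that is not continued as stable background therapy under inclusion 4d, which matches the condition already in SLE Table 6. Leave pSS 5dd as it is.

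Before unblinding, state in the rules for the Per Protocol Set that stable background MTX meeting 4d is not an eligibility deviation.

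The cost is one clause, by amendment or administrative letter, and one sentence in the deviation rules.

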- bb) Previous exposure to BTK inhibitors such as ibrutinib, acalabrutinib, or experimental drugs such as tirabrutinib, vecabrutinib, zanubrutinib, ARQ-531, GDC-0853, or any others
- cc) Required discontinuation periods for immunomodulatory drugs (other than HCQ), eg, cyclosporine, tacrolimus, etc, or biologic drugs (including those specifically listed below) are detailed in pSS Table 6. If a drug is not specifically listed, consult the Medical Monitor for guidance. Usual discontinuation periods are 4 weeks or 5 half-lives whichever is longer.
- dd) Treatment with DMARDs (excluding HCQ) or immunomodulators beyond required washout period before randomization; MTX treatment within 12 weeks before randomization or during the study. **HCQ whole blood concentration >2 μg/mL (at screening only) is exclusionary**. HCQ dose > 400 mg/day, new initiation, or dose increases during treatment are not permitted.
- ee) Administration of all live vaccines is prohibited within 90 days before randomization. Administration of inactivated vaccines and nonlive vaccines, including those for influenza and SARS-CoV-2, is prohibited within 30 days before randomization. See Section pSS Table 6 for corresponding on-treatment and posttreatment restrictions.

6) Physical and Laboratory Test Findings: pSS Sub-protocol

- a) Clinically significant abnormalities on chest x-ray or ECG
- b) Clinically significant abnormalities in laboratory tests including the following:
 - i. Serum ALT $> 2 \times$ ULN, unless explicitly related to the indication based on the investigator's judgment.
 - ii. Serum AST > 2× ULN, unless explicitly related to indication based on the investigator's judgment.
 - iii. Serum total bilirubin > 1.5× ULN (does not apply to subjects with Gilbert's syndrome)
 - iv. Hemoglobin $\leq 8 \text{ g/dL}$ ($\leq 80 \text{ g/L}$)
 - v. Proteinuria > 3.0 g/day (> 3,000 mg/day) or equivalent level of proteinuria as assessed by UPCR (3 mg/mg or 339 mg/mmol)
 - vi. $eGFR < 50 \text{ mL/min/}1.73 \text{ m}^2$ as calculated by the central laboratory

- vii. Serum creatinine > 2.0 mg/dL (> 177 μmol/L)
- viii. Absolute WBC count $< 2.5 \times 10^3 / \mu L$ ($< 2.5 \times 10^9 / L$)
 - ix. Absolute neutrophil count $< 1000/\mu L$ ($< 1.0 \times 10^9/L$)
 - x. Platelet count $< 100 \times 10^{3} / \mu L$ ($< 100 \times 10^{9} / L$)

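### SLE exclusion 6b(x) attaches an allowance-type qualifier to a platelet exclusion, so read literally its numeric limit covers only SLE-related low counts without increased bleeding risk

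*Combined protocol and SAP*

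**What the plan says.** SLE 5.2 opens with "An individual who meets any of the following criteria will be excluded from participation in" the sub-protocol, so each item describes people who are kept out. Section 6b introduces its laboratory items with "Clinically significant abnormalities in laboratory tests including the following". Item 6b(x) then gives a platelet count below 75 × 10^9/L and adds "if considered part of SLE disease activity without increased risk of bleeding". The item is current; it carries no label retiring it under an earlier revision.

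Other provisions bear on the same subjects:

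- Item 6b(iv), hemoglobin: below 8 g/dL, "or, if due to hemolytic anemia related to SLE, < 7 g/dL".
- Item 6c: "Any other significant laboratory or procedure abnormalities that, in the opinion of the investigator, might pose unacceptable risk to the subject during the study".
- Item 1a: "Any major illness/condition or evidence of an unstable clinical condition (eg, renal, hepatic, hematologic", and further examples, where the investigator judges that participation would substantially raise the subject's risk.
- Item 1(l): any other sound reason, as the investigator determines.
- SLE 5: the Medical Monitor or the lupus central review service checks and confirms each subject's eligibility before randomization.

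The corresponding pSS item, pSS 5.2 6b(x), excludes platelets below 100 × 10^9/L with no condition attached.

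**The concern.** The qualifier reads like the wording of an allowance: it describes low counts that a protocol might choose to tolerate. Joined by an if to an exclusion, it does the opposite and makes those counts the only ones the limit excludes. A subject whose low platelets come with increased bleeding risk falls outside the item.

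This is an eligibility safety limit, so its literal meaning matters. SLE 5 insists that every randomized subject satisfy all the criteria, and SLE 8 rules out waivers. A site or central reviewer who suspects that the item means something other than what it says therefore has no waiver to fall back on. The case can plausibly arise, because the SLE rationale names hematologic involvement among the manifestations of the disease.

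**Working it through.** No arithmetic applies. The check sets the item against every combination of its two conditions and then against its neighbors.

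**Step 1. Literal reading.** Take a subject with platelets below 75 × 10^9/L, for example 60 × 10^9/L.

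| Cause of low count | Increased bleeding risk | Outcome under SLE 6b(x) as written |
|---|---|---|
| SLE | No | Excluded |
| SLE | Yes | Not captured |
| Other | No | Not captured |
| Other | Yes | Not captured |

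One of four combinations meets a numeric limit and three do not.

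**Step 2. Is there another platelet limit?** The SLE sub-protocol gives no other numeric platelet limit. SLE Table 7 lists platelet count only as a test to be run.

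**Step 3. How neighboring items are built.** Where these lists make room for a cause-related exception, they state the limit first:

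- Hemoglobin, SLE 6b(iv): a general limit of 8 g/dL, then a separate limit of 7 g/dL for SLE-related hemolytic anemia.
- Bilirubin, SLE 6b(iii): a limit of 1.5 times the upper limit of normal, then a carve-out for Gilbert's syndrome.
- ALT and AST, pSS 6b(i) and (ii): a limit of 2 times the upper limit of normal, then a carve-out for elevations tied to the indication.

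SLE 6b(x) has only a conditional branch. It has no general limit, and its condition narrows the exclusion where the others state an exception to it.

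**Step 4. What the possible intents would do.** The documents do not state the intent. Two candidates show how far the decision depends on it:

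- *The qualifier was meant as an exception.* The first row would not be excluded and the other three would be. All four outcomes differ from the literal reading.
- *A general limit was dropped, as if from an item built like hemoglobin.* Assuming that the lost general limit was no lower than 75 × 10^9/L, all four rows would be excluded. Three of the four outcomes differ from the literal reading.

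Under either candidate, the three uncaptured combinations change outcome. The first row is excluded under one and not excluded under the other.

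**The case against.** The strongest reply is that nobody has to be enrolled because of this wording. The 6b stem is open-ended, so a clinically significant low platelet count can be excluded there whatever its cause. Items 6c, 1a and 1(l) give the investigator further grounds, and every subject's eligibility is confirmed beyond the site before randomization. This stands. A reader might infer that a subject at 60 × 10^9/L with non-SLE thrombocytopenia is eligible; the most that can be said is that 6b(x) does not exclude that subject. The reply does not repair the item, because these provisions supply judgment and no number. They also leave in place the literal exclusion of SLE-related low counts without increased bleeding risk.

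Other tempting extensions are not supported:

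- *The item keeps out lower-risk subjects and lets in higher-risk ones.* One uncaptured combination is another cause without increased bleeding risk. Nothing in the documents ranks it above the captured combination.
- *Sites will apply the item differently.* They may, but no evidence shows that they will, and the central eligibility check should limit variation.
- *The exclusion of anticoagulants and antiplatelet drugs shows a bleeding policy that 6b(x) contradicts.* SLE 5.2 item 5t gives no reason for that exclusion. Master Protocol Table 1 lists dabigatran and rivaroxaban as usable up to stated doses. The documents are not consistent on this subject and cannot carry the inference.
- *SLE and pSS should share one platelet limit.* These are separate sub-protocols, and other laboratory items differ between them. The pSS item shows only that an unconditional limit is written elsewhere in the protocol.

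**Conclusion.** The point holds as a drafting defect in a stated safety criterion. As written, 6b(x) puts a numeric limit on one of four combinations of cause and bleeding risk below 75 × 10^9/L and leaves three to judgment. Comparison with 6b(iv) suggests that the item is inverted or incomplete, but that is an inference from drafting pattern; the protocol does not state the intent.

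The conclusion rests on reading the qualifier as a condition on the exclusion, which is its plain grammar, and on there being no other numeric platelet limit in the SLE sub-protocol. The number of subjects affected is not in the documents and cannot be derived from them. Sample size and the planned analyses do not change.

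**What to change.** The sponsor should reconcile the qualifier in SLE 5.2 6b(x) with its place in an exclusion list and reword the item. The new text should state unambiguously which subjects below the count are excluded and whether SLE-related counts are treated differently. The sponsor's clinicians decide the rule and the values; none is proposed here, and the SLE value need not match the pSS value.

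The cost is one line in the eligibility criteria, made by amendment.
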